4 ANALYSIS SETS

4.1 Definitions of analysis sets

Unless not relevant, i.e., for the Screened analysis set (SCR), or otherwise specified, summary statistics will be provided according to assigned treatment [as described in Section 8.1.1], which may differ from the treatment administered.

4.1.1 Screened analysis set

The SCR includes all subjects who provided informed consent and received a subject identification number.

4.1.2 Randomized analysis set

The Randomized analysis set (RND) includes all subjects from the SCR who have been assigned to a study treatment (i.e., have a randomization number).

4.1.3 Full analysis set

The Full analysis set (FAS) includes all subjects from the RND who have been administered the study treatment.

To adhere to the intention-to-treat principle as much as possible:

- Subjects are evaluated according to the study treatment they have been assigned to (which may be different from the study treatment they have received), and
- All available data are included.

If a subject is unblinded during the study, he/she will be included in the FAS.

4.1.4 Per-protocol analysis set

The Per-protocol set (PPS) comprises all subjects from the FAS who complied with the protocol sufficiently to allow adequate estimation of the treatment effects.

Criteria for sufficient compliance include exposure to treatment, availability of primary PD endpoint assessments and absence of protocol deviations that have an impact on the treatment effect.

The full list of criteria (protocol deviations and other reasons for exclusion) will be established prior to clinical database lock and is detailed in [Appendix B](#).

4.1.5 Safety analysis set

The Safety analysis set (SAF) includes all subjects who received at least one dose of study medication.

Subjects will be evaluated according to the actual treatment they received, which may differ from the randomly assigned treatment.

4.1.6 Pharmacokinetic analysis set

The PK analysis set includes all subjects from the SAF who have at least one plasma concentration measurement after administration of study treatment.

Subjects in the PK set will be evaluated according to the actual treatment they received, which may differ from the randomly assigned treatment.

4.2 Usage of the analysis sets

The analysis sets used for statistical analyses of specific variables are shown in [Table 2](#). Subject data listings were prepared using the SCR, unless otherwise specified.

Table 2 Analysis datasets usage

Analyses	Analysis sets					
	SCR	RND	FAS	PPS	SAF	PK set
Subject disposition	X					
Protocol deviations, analysis sets	X					
Demographics characteristics		(x)	X	(x)		
Medical history and current medical conditions			X			
Previous and concomitant medications			X			
Study treatment exposure			X	(x)	X	
Main (primary) PD endpoints			X	(x)		
Other PD endpoints			X			
Safety endpoints					X	
PK endpoints						X

X: main analysis, (x): Sensitivity analysis to be conducted only if > 10% difference of set size with set used for main analysis. FAS, Full analysis set; PD, pharmacodynamic(s); PK, pharmacokinetic(s); PPS, Per-protocol set, RND, Randomized analysis set; SAF, Safety analysis set; SCR, Screened analysis set.

The decision to perform a sensitivity analysis will be taken prior to any data unblinding, i.e., prior to database lock, during a blind data review.

5 STUDY SUBJECTS, VARIABLES AND ANALYSES

For categorical variables, the incidence of subjects by category will be summarized (frequency counts and percentages). While for continuous variables, summaries will use the following descriptive statistics, unless stated otherwise: arithmetic mean, standard deviation (SD), minimum, 1st quartile, median, 3rd quartile, and maximum.

In addition to the treatment groups reporting as indicated in the sections below, summaries will report results for the *Total ACT-246475* group, which combines subjects from the two ACT-246475 dose groups.

5.1 Subject disposition

5.1.1 Screening failures

The standard definition of screening failure, as described in Section 10.2.7, is used.

Summary of subjects by screening status (failure vs randomized), by country and by center will be provided using planned randomization groups instead of using the study treatment arm label, as described in Section 8.1.1.

The number (%) of subject by reasons for screening failures will be tabulated and listed.

5.1.2 Study completion/discontinuation

The definition of study premature discontinuation as described in Section 10.2.8 is used.

The date and the reason for study discontinuation are collected in the “Study Discontinuation” form (and in the “Death” form if the subject died).

Summary of subjects by study completion status (completing study vs premature discontinuation), and distribution by reason for premature study discontinuation will be provided.

5.1.3 Study treatment completion/ discontinuation

Not applicable.

5.2 Protocol deviations

Subjects with at least one protocol deviation, overall and important, will be summarized for the entire study and by study period (Screening, on study treatment, and safety follow-up).

This will be repeated by country and site.

Subjects will be counted once in each summary, i.e., if a subject has more than 1 protocol deviation for a given category/sub-category, he/she will be counted only once in summaries for this category/sub-category.

A listing will present the subjects for whom the randomization code was broken at site or sponsor office. It contains the date of unblinding and the reason for unblinding.

Subjects’ protocol deviations will be listed. This listing will include all deviation descriptions, identifiers and categories. Subjects without any protocol deviations are not included in this listing.

5.3 Inclusion in / exclusion from analysis sets

5.3.1 Subject disposition

A summary table will present an overview (frequency and percentage) of the recruitment for each country and site, by treatment group and overall.

The subjects’ disposition (frequency and percentage) will be summarized for the SCR by treatment group and overall for the defined analysis sets.

If some subjects were administered incorrect study treatment (i.e., assigned treatment is not the received one), the subject disposition summary will also be provided by the actual treatment received.

The reason for exclusion of subjects from each analysis set will be listed.

5.4 Subject characteristics

In addition to the treatment groups to report as indicated in below sections, summaries will report results for the *Total ACT-246475* group, which combines subjects from the two ACT-246475 dose groups.

5.4.1 Demographics

The following demographic characteristics are collected on the ‘Demographics’, and ‘Body Weight and Height’ electronic Case Report Form (eCRF) pages.

- Age (years)
- Sex category: *Male and Female*
- Race group: *American Indian or Alaska Native, Asian, Black or African American, Native Hawaiian or other Pacific Islander, White, Other, Not applicable*
- Ethnic category: *Hispanic or Latino, Not Hispanic or Latino, and Unknown*
- Body weight (kg)
- Height (cm)
- Country of the site (assigned in the eCRF based on the list of sites)

In addition, the following variables are derived:

- Age group: *18 to < 65, ≥ 65 to < 85, and ≥ 85 years*
- Age group: *< 55 and ≥ 55 years*
- Body mass index (BMI; kg/m²)
- BMI category: *< 25, ≥ 25 to < 30, and ≥ 30.0 kg/m².*

BMI will be computed using the following formula: BMI (kg/m²) = body weight / height², with weight expressed in kilograms, and height in meters.

The analysis described in this section will be replicated by gender using the FAS.

5.4.2 Baseline disease characteristics

Not applicable.

5.4.3 Other baseline characteristics

Other baseline characteristics, collected during Screening include childbearing potential status at Screening and contraceptive methods.

These are defined as collected on the eCRF (‘Demographics’ and ‘Contraceptive Methods’ forms respectively) and no derivation is required.

Subjects with childbearing potential at Screening, and contraceptive methods, will be listed.

5.4.4 Previous and concomitant medical history

For all the medical history, the incidence of subjects with the event will be summarized (frequency counts and percentages) by system organ class (SOC) and/or preferred term (PT).

In addition to medical history, specific medical history events or intervention dates related to the following, are collected as predefined categories:

- Myocardial infarction (MI)
- Stroke
- Transient ischemic attack (TIA)
- Percutaneous coronary intervention (PCI)
- Coronary artery bypass graft (CABG)
- Peripheral vascular surgery

For those specific medical history variables, the incidence of subjects by category and sub-category, as defined below, will be summarized (frequency counts and percentages).

CAD-related conditions: MI, PCI, and CABG

Other medical conditions: Stroke, and TIA

Risk factors: diabetes mellitus, chronic kidney disease, hypertension, and dyslipidemia

Note that dyslipidemia is not predefined in the eCRF and will have to be retrieved from medical and concomitant medical history using the MedDRA SMQ “*Dyslipidaemia*”.

Also, the incidence of diabetes mellitus or chronic kidney disease at baseline will be summarized (frequency counts and percentages).

Diabetes mellitus is any medical history observation with MedDRA PT belonging to MedDRA high level group term (HLGT) “*Diabetes mellitus (incl. subtypes)*”, existing prior to, and ongoing on day of, informed consent signature.

Chronic kidney disease is any medical history observation with MedDRA PT belonging to MedDRA SMQ “*Chronic kidney disease*”, existing prior to, and ongoing on day of, informed consent signature.

5.4.5 Previous and concomitant therapies

In this study, only medications are to be collected.

The following categories [see Section 10.7 for definition] will be considered for analysis:

- Previous medications,
- Study-concomitant medications,

- Study-treatment concomitant medications at baseline,
- Study-treatment concomitant medications.

Oral P2Y₁₂ receptor antagonists at baseline include any study-treatment concomitant medications at baseline with Anatomical Therapeutic Chemical (ATC) code included in the following list, and administered on the day of start of study medication:

Table 3 Oral P2Y₁₂ receptor antagonists

ATC code	Ingredient name
B01AC04	clopidogrel
B01AC05	ticlopidine
B01AC22	prasugrel
B01AC24	ticagrelor

ATC, Anatomical Therapeutic Chemical.

Ticlopidine, although listed in the table above, it is not expected to be used and therefore not included in categories of anti-platelet aggregation therapies defined below. However, all anti-platelet aggregation therapies will be listed.

For study-treatment concomitant medications at baseline, study-treatment concomitant medications, and oral P2Y₁₂ receptor antagonists at baseline categories, the incidence of subjects with a medication will be summarized (frequency counts and percentages) by ATC code corresponding INN.

All previous/concomitant medications will be listed.

The number and proportion of subjects with such a study-treatment concomitant medication at baseline will be summarized (frequency counts and percentages) by the following categories:

1. No aspirin/acetylsalicylic acid nor P2Y₁₂ antagonist
Study-treatment concomitant medications at baseline (based on ingredient list)
Do not include aspirin/acetylsalicylic acid **or** clopidogrel **or** prasugrel **or** ticagrelor
2. Aspirin/acetylsalicylic acid monotherapy
Study-treatment concomitant medications at baseline (based on ingredient list)
Include aspirin/acetylsalicylic acid **and** do not include clopidogrel **or** prasugrel **or** ticagrelor
3. P2Y₁₂ receptor antagonist monotherapy at least one, and for each drug: clopidogrel, prasugrel, and ticagrelor
Study-treatment concomitant medications at baseline (based on ingredient list)
4. Dual anti-platelet therapy (DAPT): aspirin/acetylsalicylic acid and clopidogrel

Study-treatment concomitant medications at baseline (based on ingredient list)
Include aspirin/acetysalicylic acid **and** clopidogrel

5. DAPT: aspirin /acetysalicylic acid and ticagrelor

Study treatment concomitant medications at baseline (based on ingredient list)
Include aspirin/acetysalicylic acid **and** ticagrelor

6. DAPT: aspirin/acetysalicylic acid and prasugrel

Study treatment concomitant medications at baseline (based on ingredient list)
Include aspirin/acetysalicylic acid **and** prasugrel

7. DAPT: any combination

Study treatment concomitant medications at baseline (based on ingredient list)
Include aspirin/acetysalicylic acid **and** clopidogrel **or** prasugrel **or** ticagrelor

5.4.6 Other subject characteristics

Not applicable.

5.5 Study treatment exposure and compliance

5.5.1 Exposure

The number and percentage of subjects by study drug administration status (administered vs not administered) will be provided.

In addition to the initial analysis set defined in the protocol (i.e., the FAS), this analysis will also be provided using the SAF.

5.5.2 Compliance with study treatment

Not applicable.

6 EFFICACY VARIABLES AND ANALYSES

6.1 Overview

Not applicable.

6.2 Primary endpoint analysis

Not applicable.

6.3 Key secondary endpoint analysis

Not applicable.

6.4 Other efficacy endpoint analysis

Not applicable.

6.5 Analysis of quality of life variables

Not applicable.

6.6 Analysis of pharmacoeconomic variables

Not applicable.

6.7 Analysis of epidemiological measures and risk-benefit evaluations

Not applicable.

6.8 Analysis of pharmacodynamic variables

For categorical variables, the incidence of subjects by category will be summarized by using frequency counts, percentages and the corresponding 95% confidence interval (CI) when relevant.

Continuous variables will be summarized using: arithmetic mean, SD, minimum, 1st quartile, median, 3rd quartile, maximum, and 95% CI of the mean when relevant.

6.8.1 Primary pharmacodynamic endpoint

6.8.1.1 Variable

The primary PD endpoint is the *PD response* that is defined for each subject as a PRU < 100 starting 30 min after injection and lasting for at least 3 h, as measured via VerifyNow®.

The primary PD variable is the platelet reactivity as measured by VerifyNow® at each time point [see tables of assessments in the protocol: table 2 and table 3].

The analysis variable of the PD response is defined as follows for a given subject:

IF maximum of (PRU_{30m}, PRU_{1h}, PRU_{2h}, PRU_{4h}) < 100

AND (no more than 1 intermediate value (PRU_{1h} or PRU_{2h}) missing)

THEN PD response = YES

ELSE PD response = NO

Where PRU_{30m}, PRU_{1h}, PRU_{2h}, and PRU_{4h} refer to PRU measured by VerifyNow® at 30 minutes, 1, 2 and 4 hours after study drug administration. Time is based on planned time point and not on the actual collection time.

Supportive primary PD endpoint estimands

To assess robustness of results, two additional PD endpoints (estimands) will be defined for sensitivity analysis. The first endpoint, noted PD response[#], will be based on the same

algorithm as described above but using the actual collection time to define the following time windows:

Table 4 Time windows definitions

Collection time point (nominal) (time post study drug administration)	Time from PRU _{30m} (assessment of response, i.e., PRU < 100)	Time windows (~ 5% margin) (min. from study drug administration)
15 minutes	-	14 to 16
30 minutes	0	28 to 32
1 hour	30 minutes	57 to 63
2 hours	1.5 hours	114 to 126
3.5 hours*	3 hours	199 to 221
4 hours	3.5 hours	228 to 252
8 hours	7.5 hours	456 to 504
24 hours	23.5 hours	1368 to 1512

* no blood sample is taken at that time point, therefore no PRU value reported.
PRU, P2Y₁₂ reaction units.

The second endpoint, in the event of frequently missing PRU_{1h} or PRU_{2h} values, $\geq 10\%$ missing values overall, noted PD response*, will consider only the 30 minutes and 4 hours post study drug administration time points:

*IF maximum of (PRU_{30m}, PRU_{4h}) < 100
AND none of those values is missing
THEN PD response* = YES
ELSE PD response* = NO*

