10.3.2.2 Handling of missing data

Subjects for whom determination of the response is not possible will be counted as non-responders in the main analysis; no other imputation will be considered.

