6.8.2 Other pharmacodynamic endpoints analysis

6.8.2.1 Variables

Endpoints

Other PD endpoints include the following:

- **Extent of aggregation:** maximum platelet aggregation (MAP; %), final platelet aggregation (FPA; at 6 minutes, %) as measured by light transmission platelet aggregometry (LTA).

- **Absolute PRU values (for VerifyNow®) at each measured time point.**
- % of subjects at 8 h after study treatment injection with PRU value < 100 or $< 0.95 \times \text{PRU baseline value}$ if PRU baseline < 100 (i.e., platelet aggregation status 8 hours after study drug administration).

The following exploratory endpoints will also be considered in the PD analysis:

- IPA (noted IPA-V) as measured by VerifyNow®, data for this endpoint will be available only for some centers.

A supportive PD endpoint is defined in the protocol statistical section for LTA-PD response. However, the exact definition of the endpoint is not provided. Therefore, the following definition will be considered for defining LTA-PD response: an IPA-M of at least 50% starting 30 minutes after injection, lasting at least 3 hours, and not exceeding the 8th hour after study drug administration for subjects with value above.

Variables

The variable of *extent of aggregation* (MPA) is used as reported in the eCRF, and is expressed as a percentage.

The *absolute PRU* variable is the actual PRU value as reported by VerifyNow®, at each time point [see protocol table 2 and table 3], and is expressed as a number without unit (the higher the number, the less IPA).

The *subject platelet aggregation status 8 hours after study drug administration* variable is defined as binary with value determined as per the following algorithm:

IF ($\text{PRU}_{\text{baseline}} \geq 100$ AND $\text{PRU}_{8h} < 100$) OR ($\text{PRU}_{\text{baseline}} < 100$ AND $\text{PRU}_{8h} < 0.95 \times \text{PRU}_{\text{baseline}}$)
THEN status = YES
ELSE status = NO

The variable of the *IPA by VerifyNow®* (IPA-V) is the value reported in the eCRF, and is expressed as a percentage. All analyses conducted on this variable will exclude missing values.

The LTA-PD response variable is defined as:

IF minimum of (IPA-M_{30m} , IPA-M_{4h}) $\geq 50\%$
AND none is missing
THEN LTA-PD response = YES
ELSE LTA-PD response = NO

The variable *IPA-M at time t* (noted IPA-M_t) is expressed as a percentage, and defined as:

$$\text{IPA-M}_t = (1 - \text{MPA}_t / \text{MPA}_{\text{baseline}}) \times 100.$$

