6.8.3 Handling of missing data

Subjects for whom determination of the PD response is not possible will not be included in the computation of response rate for the main analysis, however they will be counted as non-responders in the sensitivity analysis.

No other imputations are planned.

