Appendix B Protocol deviation list

The actual list of protocol deviation leading to exclusion from analysis set will be updated prior to study closure if required.

Table below provides the reason considered for excluding subjects from analysis set.

Table 7 Definition of exclusions from analysis sets

Analysis set	Reason for exclusion from analysis set	Programming conditions
Screened analysis set	Informed consent not initially obtained for the study	DV.DVREFID = IPD1D1
Randomized analysis set	Subject does not have a randomization number	Not in DS.RANDNO
Full analysis set	Subject did not get study treatment	EX.EXDOSE not >0
Safety set	Subject did not get study treatment	EX.EXDOSE not >0
Per-protocol set	Previous exposure to investigational drug	DV.DVREFID = IPD2A6
	Subject with platelet disorders at Screening	DV.DVREFID = IPD2A9
	Initiation or change in dose of oral P2Y12 during study	DV.DVREFID = IPD2D1
	Incorrect administration of study drug	DV.DVREFID = IPD2E1 or IPD3C1
	Deviation from study drug preparation instructions	DV.DVREFID = IPD2E2
	Incorrect blood sampling for platelet assays	DV.DVREFID = IPD2F2
	Background oral antiplatelet therapy not stable for 1 month prior to randomization	DV.DVREFID = IPD2A1
	Subject does not have stable coronary artery disease	DV.DVREFID = IPD2A3
	At least one post-dose VerifyNow® blood sample not evaluable (excluding the 24 h post dose)	at least one missing LB.LBSTRESN where LB.LBTESTCD= "P2Y12RU" and LB.LBTPT in (15 MIN POST-DOSE, 30 MIN POST-DOSE, 1 HOUR POST-DOSE, 2 HOURS POST-DOSE, 4 HOURS POST-DOSE, 8 HOURS POST-DOSE)
	Subject taking OATP1B1 and/or OATP1B3 inhibitor (systemic route) at Screening	DV.DVREFID = IPD2A7
PK analysis set	Subject has no plasma concentration measurement after administration of study treatment	all PC.PCSTRESC = « » when PC.PCTPT not PRE-DOSE

ICF, informed consent form; OATP, organic anion transporting polypeptide; PK, pharmacokinetic(s).

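### The coded rule for the primary PD response does not require the 30-min and 4-h PRU values, so a subject lacking either can be counted as a responder; probably an omitted clause

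*SAP*

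**What the plan says.** The endpoint in words (Protocol 6.2.1 and 10.2.4.2, SAP 6.8.1.1) is a PRU below 100 from 30 min after injection, held for no less than 3 h.

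The coded rule in SAP 6.8.1.1 has two conditions for YES. The maximum of the PRU at 30 min, 1 h, 2 h and 4 h must be below 100, and "no more than 1 intermediate value" may be missing, where intermediate means the 1-h or 2-h PRU. Everything else is NO. The 30-min and 4-h values (the anchors, below) carry no missingness condition.

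Related text:

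- **PD response\*** (SAP 6.8.1.1) uses only the 30-min and 4-h values and adds "AND none of those values is missing".
- **LTA-PD response** (SAP 6.8.2.1) uses the same two times and adds "AND none is missing".
- **PD response#** (SAP 6.8.1.1) keeps the primary rule: the same "algorithm as described above but using the actual collection time to define the following time windows".
- **SAP 6.8.3**: subjects whose response cannot be determined "will not be included in the computation of response rate for the main analysis". It does not say when that is the case.
- **Protocol 10.3.2.2**: such subjects "will be counted as non-responders in the main analysis".

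**The concern.** The two anchors carry the endpoint. SAP Table 4 notes that no sample is taken at 3.5 h, so the 4-h PRU is the only value in the rule taken 3 h or more after the 30-min value. Without it, the longest observed span is 30 min to 2 h, or 1.5 h. Without the 30-min value, the onset is not observed. In either case the rule can return YES when the defining property has not been seen.

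What is at stake is the primary response rate on the FAS and its test against 70%. Among subjects missing an anchor, the rule can only raise the coded rate relative to requiring both anchors. A programmer who follows 6.8.1.1 literally and one who sends these subjects to 6.8.3 would also obtain different primary results from the same data.

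**Working it through.** **1. How the maximum treats missing values.** The SAP does not say. If any missing value made the maximum missing, only complete profiles could be YES and the tolerance for one intermediate value would have no effect. The tolerance works only if the maximum is taken over observed values.

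**2. Patterns.** Four values, each present or missing, give 2^4 = 16 patterns. Suppose every observed value is below 100.

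- YES unless both the 1-h and 2-h values are missing: 3 × 4 = 12 patterns.
- Of these, both anchors are present in 3 (complete, 1 h missing, 2 h missing).
- The other 12 − 3 = 9 lack one or both anchors. The extreme case is a single observed 1-h or 2-h value.

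With both anchors required, YES falls from 12 patterns to 3. This counts patterns, not subjects: 7 of the 9 need at least two of the four samples missing.

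**3. The plan's own sample size.** Protocol 10.5 gives 98 per arm for 70% versus 85%, two-sided 0.025, power 0.9:

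n = [(2.2414 × √0.21 + 1.2816 × √0.1275) / 0.15]² = 97.98, so 98.

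98 × 1.1 = 107.8, so 108 per arm. Both figures reproduce.

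**4. Passing mark.** SAP 6.8.1.2 tests each dose one-sided at 0.025, so z must exceed 1.96, with z = (x/n − 0.70) / √(0.21/n).

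| Responders / n | z | Result |
|---|---|---|
| 84/108 | 1.76 | fail |
| 85/108 | 1.97 | pass |
| 80/103 | 1.70 | fail |
| 81/103 | 1.91 | fail |
| 82/103 | 2.13 | pass |

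**5. Threshold example (counts assumed).** One arm of 108 has 80 confirmed responders, 23 confirmed failures and 5 subjects missing only the 4-h value with all other values below 100. The literal rule gives 85/108, a pass. Exclusion under SAP 6.8.3 gives 80/103, a fail.

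**6. How often the verdict differs.** With 5 such subjects, it differs from exclusion only at 80 or 81 confirmed responders among the other 103. With 2, it differs only at 83 among 106 (83/106, z = 1.87, fail; 85/108, pass). Binomial probabilities:

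| True rate | 5 such subjects | 2 such subjects |
|---|---|---|
| 85% (design target) | 3.5% | 1.7% |
| 80% (assumed) | 16.9% | 8.5% |
| 70% (null) | 3.4% | 1.5% |

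**7. False-positive rate per dose at a true 70%.** Let m be the share of subjects missing an anchor and f the share of failures that occur only at the missing time point. The coded rate is 0.70 + 0.30 × f × m, and the rejection probability is P(X ≥ 85 of 108). With f = 0 it is 2.8%, which comes from the z-test itself. With f = 0.5 it is 3.0%, 3.3% and 4.0% at m = 1%, 2% and 5%. Both f and m are assumptions.

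**The case against.** **The rule names four values and one tolerance, so nothing else may be missing.** That is very likely the intent, and the word intermediate points the same way. But the text does not say it, while the two sibling rules do. A reader might infer that the SAP deliberately counts unobserved responses as successes. The documents do not support that; they support an omission.

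**SAP 6.8.3 catches these subjects.** It may have been meant to, since a missing anchor with all else below 100 is the natural case. But it is not linked to the rule, does not define when determination is impossible, and the IF/ELSE returns YES or NO for everyone.

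**The sensitivity analyses cover the gap.** Partly. PD response\* requires both anchors. One might infer from 6.8.1.1 that it runs only if at least 10% of 1-h or 2-h values are missing, but 6.8.1.3 plans it without that condition, so the SAP is inconsistent on this. The per-protocol set drops anyone with a missing value from 15 min to 8 h (Appendix B, Table 7). Its repeat is conditional on set size: "Sensitivity analysis to be conducted only if > 10% difference of set size with set used for main analysis". That trigger pools all exclusion reasons, so it could be met with fewer than 10% of anchors missing; 6.8.1.3 words it differently. None of these alters the main FAS analysis.

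**NO when both intermediate values are missing.** It is tempting to call this a second error, since PD response\* gives YES if both anchors are below 100. It is what the rule expressly states, and changing it would be a preference.

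**The effect is small.** This stands.

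**Conclusion.** The concern holds for the text of the coded rule. The clause requiring both anchors is absent, and the only reading that gives the stated tolerance any effect codes a subject lacking an anchor as YES when all observed values are below 100.

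Confidence is high on the missing clause and not on its effect. The documents give no anchor-missing rate, only an allowance of about 10% for drop-out and non-evaluable data together (Protocol 10.5). A reader might infer that the primary result will be materially inflated. The figures do not support that: the verdict changes only near the passing mark, and at the design target with 5 such subjects in an arm it differs from exclusion 3.5% of the time.

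It should still be fixed, because it leaves the primary endpoint open to two derivations. Whether undetermined subjects are excluded (SAP 6.8.3) or counted as non-responders (Protocol 10.3.2.2) is a separate conflict and adds no weight here.

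**What to change.** In SAP 6.8.1.1, for PD response and PD response#:

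1. Add to the YES condition that the 30-min and 4-h PRU are both non-missing, and state that the maximum is taken over observed values.
2. Code NO if any observed value from 30 min to 4 h is 100 or higher.
3. Define subjects missing an anchor with all observed values below 100 as undetermined, and name them in SAP 6.8.3 as the group it refers to.
4. Keep the stated NO for subjects missing both intermediate values, unless the sponsor chooses otherwise before unblinding. Say that this takes precedence when an anchor is missing too. The 16 patterns with all observed values below 100 then split into 3 YES, 9 undetermined and 4 NO.

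Reconcile separately how the undetermined group is counted (SAP 6.8.3 against Protocol 10.3.2.2), and whether PD response\* is conditional (SAP 6.8.1.1 against 6.8.1.3).

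The cost is small: one clause and a three-level derivation in the SAP and its program. No new data are needed.
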